4.2 Methods and Timing for Assessing, Recording, and Analyzing Safety Parameters

Safety will be assessed throughout the clinical trial to all subjects who has received any amount of the investigational product (AT-III [Human] or Placebo). See [Section 5.1.4](#).

4.2.1 Adverse Events

Adverse events (includes adverse reactions [AR]) occurring at any time between signing of the subject's ICF and the last day of the subject's participation in the clinical trial will be reported and recorded on the appropriate subject's eCRF entry.

It is the Investigator's responsibility to ensure that all AEs are appropriately recorded.

Adverse events will be elicited by spontaneous reporting by the study individual or by a non-leading inquiry or direct observation by the study staff.

4.2.2 Physical Examinations

A medically certified individual will conduct a physical examination at the screening visit, within 48 hours prior to the first AT-III (Human) infusion, at ICU admission, at ICU discharge, and at the follow-up visits. The findings of each examination will be recorded on the eCRF. Abnormal findings judged as clinically relevant by the Investigator will be considered AEs.

4.2.3 Vital Signs

Vital signs will be measured by a medically certified individual or a nurse according to his/her standard clinical practice. Vital signs will be measured at the Screening visit, preoperatively, at ICU admission, and during the follow-up period.

The following vital signs will be assessed:

- T
- BP (systolic blood pressure [SBP]) and diastolic blood pressure [DBP]),
- HR
- RR

Vital signs will be routinely monitored by the study staff as detailed in [Section 3.6.2](#) and [Appendix 1](#). The Investigator will be required to classify vital signs abnormalities as clinically relevant or not according to his/her criteria. Results will be recorded in source documents and on the subject eCRF. Vital signs abnormalities judged by the Investigator as clinically relevant will be considered AEs.

4.2.4 Clinical Chemistry and Hematology

All clinical laboratory data for renal (creatinine, BUN), hepatic (ALT, AST, AP and TB) and haematological parameters (CBC including differential leukocyte count) will be listed for each clinical trial subjects.

The Investigator will be required to classify laboratory results out of the normal range reported by the laboratory as clinically relevant or not according to his/her criteria.

Laboratory results out of the normal range judged by the Investigator as clinically relevant will be considered AEs.

4.3 Procedures for Eliciting Reports of and for Recording and Reporting Adverse Event and Intercurrent Illnesses

4.3.1 Adverse Events

An AE is defined as any untoward medical occurrence in a patient or clinical investigation subject administered a medicinal product or study treatment and which does not necessarily have a causal relationship with this administration. An AE can therefore be any unfavorable and unintended sign (including any abnormal laboratory findings, for instance), symptoms, or disease temporally associated with the use of a medicinal product or study treatment, whether or not considered related to the medicinal product or study treatment.

Any AE that occurs at any time between signature of the informed consent and last day of the subject's participation in the clinical safety period of the study (Follow-up visit Day 30 ± 4 days) must be reported on the AE eCRF entry.

4.3.2 Causality of Adverse Event

The investigator will be asked to assess the causal relationship of the AE to the study treatments according to the following classification based on Karch FE et al (42):

- **Definite:** An event that follows a reasonable temporal sequence from administration of the treatment or in which the treatment level has been established in body fluids or tissues; that follows a known response pattern to the suspected treatment; and that is confirmed by improvement on stopping the treatment (dechallenge), and reappearance of the event on repeated exposure (rechallenge).
- **Probable:** An event that follows a reasonable temporal sequence from administration of the treatment; that follows a known response pattern to the suspected treatment; that is confirmed by dechallenge; and that could not be reasonably explained by the known characteristics of the subject's clinical state.
- **Possible:** An event that follows a reasonable temporal sequence from administration of the treatment; that follows a known response pattern to the suspected treatment; but that could have been produced by the subject's clinical state or other modes of therapy administered to the subject.
- **Doubtful/Unlikely:** An event that follows a reasonable temporal sequence from administration of the treatment; that does not follow a known response pattern to the suspected treatment; but that could not be reasonably explained by the known characteristics of the subject's clinical state.
- **Unrelated:** Any event that does not meet the criteria above.

The operational tool to decide the AE causal relationship is based on algorithms by Karch-Lasagna and Naranjo (43, 44).

When an AE is classified, assessing causal relationship by the investigator, as definitive, probable, possible, or doubtful/unlikely, the event will be defined as suspected ADR. When the causal relationship is labeled "Unrelated", then it will be considered that the AE is not imputable to the study treatment and it is not a suspected ADR. For definition of AR, see [Section 4.3.3](#).

Any AE experienced by the subject prior to the first blinded investigational product infusion on Day 0 will be labeled as Unrelated to the study drug.

In addition, when a causal relationship between the study treatment and the AE cannot be ruled out by the Investigator, it means that the AE cannot be labeled "Unrelated"; then, the Investigator will be asked to evaluate whether the AE is attributable only to the study

treatment or also to the surgical technique employed. Potential causal relationships between an AE and the surgical technique will be evaluated.

4.3.3 Suspected Adverse Drug Reaction and Adverse Reaction

All noxious and unintended responses to a medicinal product or device related to any dose should be considered suspected ADRs. The phrase “responses to a medicinal product or device” means that a causal relationship between a medicinal product or device and an AE is at least a reasonable possibility, that is, the relationship cannot be ruled out. In the framework of this study, a suspected ADR with a causal relationship of “definite” will be named as AR. Adverse reactions are a subset of suspected ADR.

The sponsor is responsible for assessing the suspected ADR expectedness during the clinical trial.

4.3.4 Severity (Grade) of the Adverse Event

For any AE or SAE, the severity (grade) of an event must be assessed. The following guidance should be used to determine event severity:

- **Mild:** usually transient in nature and generally not interfering with normal activities. Subjects have transient symptoms; no treatment required other than non-prescription drugs.
- **Moderate:** sufficiently discomforting to interfere with (but may not overtly prevent) normal activities. Subject was symptomatic and required treatment, but had no sequela.
- **Severe:** prevents normal activities. Subject was incapable of work or usual activity; treatment with prescription medication was required and/or sequela were produced

Adverse event and suspected ADR severity (intensity) gradation must be distinguished from AE and suspected ADR seriousness gradation, which is defined according to event consequence. For example, a headache could be mild, moderate, or severe but unusually is serious in all these cases.

The investigator will be responsible for assessing the AE or suspected ADR severity (intensity) during the clinical trial, taking into account currently criteria detailed in this section.

4.3.5 Serious Adverse Event

An SAE is an AE or a suspected ADR, occurring at any dose that fulfils one or more of the following:

- results in **death**

- is immediately life-threatening (life-threatening in the definition of SAE refers to an event in which the subject was at immediate risk of death at the time of the event; it does not refer to an event which hypothetically might have caused death if it were more severe).
- requires in-subject **hospitalization** or prolongation of existing hospitalization*
- results in persistent or significant **disability** or incapacity
- is a **congenital anomaly** or birth defect
- is an important medical event: important medical event in the definition of “serious” refers to those events which may not be immediately life-threatening, or result in death, or hospitalization, but from medical and scientific judgment may jeopardize the subject and/or may require medical or surgical intervention to prevent one of the other outcomes listed above. Examples of such events are intensive treatment in an emergency room or at home for allergic bronchospasm, blood dyscrasias or convulsions that do not result in hospitalization. Development of cancer or drug dependency or drug abuse will normally be considered serious by this criterion.

*Hospitalization is to be considered only hospital stay for equal or more than 24 hours.
The following hospitalizations should not be reported as SAEs:

- Hospitalization or prolongation of hospitalization needed for procedures required by the clinical trial protocol.
- Hospitalization or prolongation of hospitalization as part of a routine procedure followed by the center.
- Hospitalization for a survey visit, annual physicals, or social reasons.
- Elective (pre-planned) hospitalizations for a pre-existing condition that had not worsened from Baseline (e.g. elective or scheduled surgery arranged prior to start of the study).
- Admissions not associated with an AE (e.g. social hospitalization for purposes of respite care).

A distinction should be drawn between serious and severe AEs. The term “severe” is used to describe the severity of a specific event; the event itself, however, may be of relative minor medical significance (such as severe headache). This is not the same as “serious”, which is defined on subject/event outcome or action criteria usually associated with events that pose a threat to a subject’s life or functioning. Seriousness (not severity) is a medical term while severity is a subjective term.

According to the medical criteria, an AE, or a suspected ADR, can be classified as serious, although it does not fulfill the conditions fixed in this section, if it is considered important from a medical point of view. The investigator is responsible for assessing the AE, or suspected ADR, seriousness during the clinical trial, taking into account currently criteria fixed in this section.

4.3.6 Expectedness of Adverse Event or Suspected Adverse Drug Reaction

An AE or suspected ADR is considered “unexpected” if the nature, seriousness, severity, or outcome of the reaction(s) is not consistent with the reference information. The expectedness of an AR shall be determined by the sponsor according to the reference document (ie, IB).

Events not listed for the particular drug under investigation in the IB are considered “unexpected” and those listed are considered “expected.” When new AE information is received, it is the sponsor’s responsibility to determine whether the event is “unexpected” for investigational new drug (IND) safety reporting purposes.

4.3.7 Adverse Event Documentation

All AEs and SAEs occurring after the subject has signed the **informed consent form (ICF)** must be fully recorded in the subject’s eCRF or SAE form. For example, a laboratory test abnormality considered clinically relevant, eg, causing the subject to withdraw from the study, requiring treatment, causing apparent clinical manifestations, or judged relevant by the investigator, should be reported as an AE. Each event must be adequately supported by documentation as it appears in the subject’s medical or case file.

At each visit, AEs will be elicited by asking the individual a non-leading question such as “Do you feel different in way since the last visit?”. Moreover, AE will also be collected through directly observed events or spontaneously volunteered by the subject. Clearly related signs, symptoms, and abnormal diagnostic procedures should preferably be grouped together and recorded as a single diagnosis or syndrome wherever possible. It is responsibility of the Investigator to ensure that AEs are appropriately recorded.

The following variables must to be recorded on the AE eCRF entry:

1. the verbatim term (a diagnosis is preferred)
2. date/time of onset
3. date/time of resolution
4. intensity (mild, moderate, severe)
5. causality (unrelated, doubtful/unlikely, possible, probable, definite)*
6. seriousness (yes, no)
7. action taken (with regard to study drug)
8. other action (to treat the event)
9. outcome and sequel (follow-up on AE)

*Causality assessment will be only made when the AE occurs after the subject has received one or another study treatment. AE occurring before subject's exposure to study treatments will be always labeled as "Unrelated".

For AEs that occur during infusions, the infusion rate in effect at the time of onset of the AE, the time of onset of the AE and the time of AE change materially in intensity and/or resolve will be captured the eCRF entry.

In addition to the Investigator's own description of the AEs, each AE will be encoded by the sponsor (or designee, eg, CRO) according to the MedDRA® dictionary of medical codes.

A pregnancy not verified before randomization but occurring during the course of the study will be not considered an AE, unless a relation to the study drug is suspected. In any case, must be completed a Pregnancy Report Form and send as soon as possible to the Sponsor, and the study treatment must be discontinued. A copy of the form should be filled at the study site for follow-up until the end of the pregnancy.

4.4 Reporting of Serious Adverse Events or Pregnancy

[figure not shown]
4.4.1 Reporting Serious Adverse Event

All SAEs must be expeditiously reported, whether or not considered attributable to the study drugs. A SAE Report Form should be used to expeditiously report the SAE to the receiver appointed.

When the Investigator becomes aware of an SAE, she/he must submit by email a complete, signed, and dated SAE Report Form **within 24 hours** to the Sponsor.

After the initial report, all relevant follow-up information for the SAE including the outcome, must be also supplied to the Sponsor in a timely manner (within 3 days from its identification or within 24 hours for relevant new information) by means of the SAE Report Form or by other appropriate means, such as data clarification form issued by the Sponsor or CRO. In addition, the Sponsor or CRO may request additional information and/or reports.

All SAE Report Forms must be reported to:

Serious adverse events will be assessed by the Sponsor or designee for expectedness assuming that all subjects have been treated with AT-III. If the event is considered serious, suspected potentially related to the study drug and unexpected (SUSAR), then the treatment allocation will be unblinded. The following possibilities resulting from the unblinding will be considered:

1. If the study drug administered to the subject is AT-III, the case will be reported in accordance to local regulations.
2. If the study drug administered to the subject is Placebo, the suspected ADR will be reassessed for expectedness according to the reference safety information and:
 - a. If the suspected ADR is still considered unexpected, it will be reported in accordance with applicable requirements and guidelines.
 - b. If the suspected ADR is considered expected, it will not be reportable on an expedited basis, unless specifically requested by local regulations.

4.4.2 Reporting Pregnancy

While pregnancy itself is not a true “AE,” pregnancy occurring in a clinical study must be followed, to collect information regarding the experiences of gestation and pregnancy with investigational product exposure. The Investigator must report any pregnancy that occurs in a study subject subsequent to informed consent until 28 days after the last dose of investigational product. Any female subject who becomes pregnant during the study will be discontinued from investigational product treatment and will be followed for pregnancy outcome.

For any pregnancy with an outcome of live birth, the newborn infant will be followed until one month of age. Any anomalies, complications, abnormal outcomes, or birth defect observed in the child must be reported as an SAE within 24 hours of the Investigator or study personnel’s first knowledge.

5 STATISTICAL METHODS AND DETERMINATION OF SAMPLE SIZE

5.1 Statistical and Analytical Plans

Unless otherwise specified, descriptive statistics will include the number of observations, mean, standard deviation (SD), median, minimum and maximum values for the continuous/quantitative data, or frequency counts and percentages for categorical/qualitative data.

Data handling and evaluation procedures will be described in the Statistical Analysis Plan.

5.1.1 Subject Population(s) for Analysis

Intention-to-Treat population (ITT) will include all subjects who are randomized.

Per-protocol (PP) population will include all ITT subjects who have no major protocol deviations.

Safety population will include all subjects who receive any amount of study drug.

5.1.2 Demographic and Baseline Characteristics

Demographic and baseline characteristics will be summarized by treatment group using ITT population. For quantitative variables, mean, SD, median, and minimum/maximum will be provided. For qualitative variables, the frequency and percentage will be provided.

5.1.3 Efficacy Analysis

5.1.3.1 Primary Efficacy Analyses

The primary efficacy variable is the percentage of subjects with any component of the composite of major morbidity. The primary efficacy variable will be analyzed with Cochran Mantel Haenszel test adjusting for history of MI using ITT population. The sensitivity analyses using PP populations will also be provided.

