3.3.3.2 Randomization

Subjects will be randomized into one of two treatment groups: AT-III (Human) treatment group and Placebo control group. Subjects will be stratified by their previous history of myocardial infarction (MI). Unblinded pharmacist or designee will obtain the treatment assignment based on a computer-generated randomization schedule. The randomization number will be assigned at Preoperative visit (Day 0) after all enrollment criteria are met.

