3.6.2.2 Screening Visit: (within Two Weeks Prior to Surgery)*

- Signed informed consent
- Allocation of Screening Number
- Inclusion/Exclusion criteria

- Addition of subject's data into Screening Log
- All clinically relevant medical case history and demographic data (age, gender, race, weight, height, body mass index [BMI], smoking habits, ejection fraction, previous MI, unstable angina, arrhythmia, cardiogenic shock, congestive heart failure, pre-existing renal failure or dialysis treatment, chronic obstructive pulmonary disease [COPD], previous stroke, percutaneous coronary interventions, previous pulmonary thromboembolism, previous IABP, diabetes mellitus requiring treatment, oral anticoagulation therapy, heparin therapy, peripheral vascular disease or systemic thromboembolism, hypertension, hypercholesterolemia, immunosuppressive treatment). Please include any relevant medical conditions as well as medical disorders requiring medication or that are currently active.
- Physical examination
- Vital signs (temperature [T], blood pressure [BP], heart rate [HR], respiratory rate [RR])
- AT activity levels (local lab) (Only for subjects undergoing isolated CABG or single valve repair/replacements and not receiving preoperative heparin [see entry criteria])
- AT activity levels (central lab)
- Hematology and coagulation (Hb, Hct, RBC, WBC, PLT, aPTT, PT, INR, fibrinogen, TAT, F1+2)
- Clinical chemistry (creatinine, total bilirubin, ALT, AST, BUN, lactate dehydrogenase [LDH], glucose, sodium, potassium, chloride and calcium)
- Serum pregnancy test (for women of childbearing potential)
- An appropriate volume of blood will be drawn in order to obtain a serum/plasma retention sample. The retention sample will be frozen and stored at -70°C and stored in the event that additional testing is required in the future for purposes of this study only (i.e. repeat testing, or confirmation of virology results).
- Documentation of medications that the subject is taking or has taken within the last month (including transfusions of blood or any blood-derived product)
- Adverse events

* The Screening visit may occur on the same day of the Prescreening visit. If a subject's surgery is scheduled to occur in ≤ 72 hours, the Prescreening and Screening visits may be combined.

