5.2 Determination of Sample Size

Assuming that percentage of subjects with major morbidity composite is 22.0% in Placebo group and 14.3% in AT-III treatment group (ie, AT-III treatment group has a 35% relative reduction comparing to the Placebo control group), 192 subjects per treatment arm (total 384 subjects) are needed to have 70% power to detect a trend at alpha = 0.15. Considering 5% dropout rate, it is estimated that 404 subjects (202 subjects per treatment arm) need to be randomized.

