10.1 Primary Efficacy Analyses

Number and Percentage of subjects with any component of a major morbidity composite will be summarized by treatment and analyzed using Cochran Mantel Haenszel test adjusting for history of MI based on mITT population. Sensitivity analyses using PP population or mITT population minus subjects with postoperative AT administration per investigator's discretion will also be provided.

Subgroup analyses by age group, gender, and surgery type (isolated CABG vs. all other surgeries per medical review of all surgical procedures) will be performed for both mITT and PP populations, as well as mITT population minus subjects with postoperative AT administration.

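### The primary composite is tested with no prognostic baseline value beyond history of MI, although age, ejection fraction and creatinine are collected; adjusting for them is a cheap improvement worth about 0 to 5 power points

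*Protocol*

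**What the plan says.** Randomization uses one stratification factor (Protocol 3.3.3.2): "Subjects will be stratified by their previous history of myocardial infarction (MI"). The primary test adjusts for that factor and nothing else. Protocol 5.1.3.1 reads "The primary efficacy variable will be analyzed with Cochran Mantel Haenszel test adjusting for history of MI using ITT population", and SAP 10.1 has the composite "analyzed using Cochran Mantel Haenszel test adjusting for history of MI based on mITT population". SAP section 13 explains the move from ITT to mITT, so the population in the protocol sentence is superseded. The test and its adjustment factor are not.

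The Screening visit (Protocol 3.6.2.2) collects "age, gender, race, weight, height, body mass index [BMI], smoking habits, ejection fraction, previous MI, unstable angina" and, in the chemistry panel, creatinine. SAP section 8 tabulates age and ejection fraction at baseline. SAP 10.1 uses age group, gender and surgery type only to define subgroups. Its sensitivity analyses change the population, not the model. The only covariate model in the plan is the ANCOVA of AT levels on baseline AT (Protocol 5.1.3.2, SAP 10.2).

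The sample size (Protocol 5.2, SAP 5.3) assumes that the "percentage of subjects with major morbidity composite is 22.0% in Placebo group and 14.3% in AT-III treatment group", and concludes that "192 subjects per treatment arm (total 384 subjects) are needed to have 70% power to detect a trend at alpha = 0.15".

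**The concern.** The composite pools death, stroke, acute kidney injury, re-exploration, thromboembolism, ventilation beyond 24 hours and infection. A patient's condition before surgery plausibly predicts several of these. The documents give some indirect support:

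- **Creatinine.** The kidney-injury component requires a creatinine above 2.0 mg/dL and twice baseline, or new dialysis. On the creatinine route, a subject starting at 0.6 mg/dL needs more than a 3.3-fold rise (2.0/0.6), while one starting at 1.0 needs about a 2-fold rise. Baseline creatinine is therefore tied to that component by definition.
- **Age.** Protocol 1.1 names advanced age, alongside heparin use and recent MI, as a cause of low preoperative AT, and links low postoperative AT to poor outcome. It also reports one study that found no clear relation between baseline AT and cardiac events.

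A CMH test on one binary factor cannot use continuous measurements. If they are prognostic, the trial gives up some power that needs no extra patients, in a design with only 70% power at alpha 0.15. It also leaves chance imbalance in these measures uncorrected.

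**Working it through.** **Inputs from the documents.** p1 = 0.22, p2 = 0.143, 192 per arm, alpha 0.15, power 0.70, 1:1 allocation. Sidedness is not stated.

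**1. Reproduce the planned size.** With z(0.925) = 1.4395 and z(0.70) = 0.5244, the two-sided unpooled formula is

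n = (1.4395 + 0.5244)² × (0.22×0.78 + 0.143×0.857) / (0.077)² = 3.857 × 0.29415 / 0.005929 = 191.4, so 192 per arm.

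The pooled-variance formula gives 193. One-sided alpha gives 122, so the plan must be two-sided. Power at 192 per arm, with a pooled variance under the null:

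(0.077×√192 − 1.4395×√(2×0.1815×0.8185)) / √0.29415 = (1.0669 − 0.7847) / 0.5424 = 0.520, so power = 69.9%.

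**2. Analytic gain from adjustment.** If the covariates explain a share R² of outcome variance beyond MI history, the variance of the adjusted risk difference is multiplied by (1 − R²), and the effective n per arm is 192/(1 − R²). The documents give no R². The assumed range below is matched to the AUC of a baseline risk score at an average event rate of about 18%.

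| Assumed R² | Approx. AUC | Effective n per arm | Power | Gain (points) | n per arm for 70% |
|---|---|---|---|---|---|
| 0 | 0.50 | 192 | 69.9% | 0 | 193 |
| 0.02 | 0.60 | 195.9 | 70.6% | 0.7 | 190 |
| 0.05 | 0.66 | 202.1 | 71.6% | 1.8 | 184 |
| 0.10 | 0.72 | 213.3 | 73.5% | 3.6 | 174 |
| 0.15 | 0.76 | 225.9 | 75.4% | 5.5 | 165 |

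(Gains are taken from unrounded power.)

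**3. Simulation check.** 384 subjects and 6,000 trials per setting. Assumed: MI prevalence 30%, MI log odds 0.3, three continuous covariates. CMH by MI was compared with a logistic model containing treatment, MI and the three covariates.

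| SD of covariate score on logit scale | CMH power | Adjusted power |
|---|---|---|
| 0 (not prognostic) | 69.0% | 68.8% |
| 0.5 (AUC about 0.64) | 70.3% | 70.9% |
| 0.75 (AUC about 0.69) | 70.7% | 73.0% |
| 1.0 (AUC between 0.73 and 0.76) | 69.7% | 74.1% |

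The Monte Carlo standard error of each power is about 0.6 points. Under the null, rejection was 14.8% to 15.9% for CMH and 15.2% to 16.1% for the adjusted Wald test (standard error √(0.15×0.85/6000) = 0.5 points). Adjusted rejection was 0.2 to 0.6 points above CMH in the same runs, so a small part of the apparent gain could come from that.

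A second simulation used 20,000 trials per setting, a likelihood-ratio test, one prognostic score with two noise covariates, and MI prevalence 35%. Its gains were 0.8, 1.3, 3.1 and 5.0 points at AUC 0.60, 0.65, 0.70 and 0.755. A test based on the standardised risk difference performed the same as the logistic test.

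**4. Events available.** 192×0.22 + 192×0.143 = 42.2 + 27.5 = 69.7, or about 70. Six slopes (treatment, MI, age, ejection fraction, creatinine, ejection-fraction-missing indicator) leave 69.7/6 = 11.6 events per slope.

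**The case against.** The strongest reply is that nothing here is wrong. A CMH test stratified by the randomization factor matches the design and tests the stated objective directly. The modest power is a declared choice in a Phase 2b study, "70% power to detect a trend at alpha = 0.15", and omitting covariates did not cause it. That stands: the point is about efficiency, not validity.

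The size of the gain is also assumed. No section says how strongly age, ejection fraction or creatinine predict this composite. Exclusion 8 removes subjects with creatinine above 2 mg/dL, which narrows that variable, and the simulations give the model a correctly specified score, which favours adjustment. This stands too, and it is why the range starts at zero.

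The change has costs. It departs from Protocol 5.1.3.1. Ejection fraction is listed as a history item without a method or time window, and its completeness is unknown. SAP section 13 reports more undosed subjects than expected, so events may number fewer than 70. These limit the model but do not rule it out. A further worry, that a logistic test and a risk-difference interval answer different questions, disappears if both rest on the standardised risk difference.

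A reader might infer that the primary test uses no patient-level baseline information at all. It does: MI history is such a factor, and both documents adjust for it. Nor would adjustment remove all chance imbalance in patient risk. It addresses only the measures in the model.

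**Conclusion.** The point holds as a cheap improvement. The composite is tested with no prognostic baseline value beyond history of MI, while three plausible ones are already collected. At 192 per arm and two-sided alpha 0.15, adjustment would add about 0 to 5 points to the planned 70%, over an assumed AUC from 0.50 (no prognostic value) to 0.75. If the covariates predict nothing, the loss is within simulation error (69.0% vs 68.8%).

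Two stronger readings are not supported. The planned test is not invalid or biased for lack of these covariates. Nor can the gain be called free or assured, because the documents contain no figure for prognostic strength and the change has real, if small, costs.

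**What to change.** Before unblinding, amend SAP 10.1 and record the change from Protocol 5.1.3.1 in SAP section 13:

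- **Model.** Fit a logistic working model with treatment, history of MI, age (continuous), ejection fraction and baseline creatinine. Use the correct MI stratum and the baseline definition already given in SAP 5.1.
- **Test and estimate.** Base both the primary test and the confidence interval on the standardised (marginal) risk difference from that model. The target stays the difference in the percentage of subjects with any component. It also supplies an effect estimate and interval, which SAP 10.1 does not name for this endpoint.
- **Missing data.** Impute a missing ejection fraction by the overall median and add a missing indicator. Exclusion 8 already requires a local creatinine result for entry.
- **Supportive analysis.** Keep the MI-stratified CMH test.
- **Limit.** Add no further covariates, given about 70 expected events for up to six slopes.

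The cost is SAP text, a documented change to the planned primary analysis, a missing-covariate rule and one model on data already collected. No patients or visits are added.
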